¹ Symptomatic patients (\geq CTCAE grade 1) must continue with questionnaires on a weekly basis while active on the treatment portion of the study.² Hematology - WBC plus differential (neutrophil including bands, lymphocyte, monocyte, eosinophil, basophil and other counts, hemoglobin and platelets).³ HbA_{1c} and C-peptide will be measured at screening and on Day 1 of every third treatment cycle starting with Cycle 2 Day 1 and at EOT.⁴ Biochemistry - K+, Na+, Ca++, Mg++, LDH, ALT, AST, total bilirubin (direct and indirect), creatinine, amylase, GGT, lipase, alkaline phosphatase (fractionated if alkaline phosphatase is grade 2 or higher), bicarbonate, phosphorus, uric acid, total cholesterol, HDL, LDL, triglycerides, glucose, urea or BUN, albumin, and total protein are required at baseline and at end of treatment. Subsequent assessments always include K+, Na+, Ca++, ALT, AST, total bilirubin (direct and indirect), creatinine, alkaline phosphatase, bicarbonate, phosphorus, glucose, urea or BUN, albumin, and total protein BUT, lipase, total cholesterol, HDL, LDL, triglycerides should be obtained on the first day of odd numbered cycles only.⁵ Coagulation - PT or INR, PTT. Patient entering the study while receiving anti-coagulation therapy or those who have the initiation of an anti-coagulation therapy should have their coagulation test performed on a weekly basis.⁶ Patients must be fasting overnight for at least 8 hours. Additional measurements may be performed as clinically indicated.⁷ Urinalysis includes macroscopic (protein, glucose, ketones, blood, and specific gravity). A microscopic (WBC/HPF, RBC/HPF, and any additional findings) exam need only be performed if the urinalysis result is abnormal.⁸ Screening radiological assessments should be performed within 4 weeks of the first dose. Radiological tumor assessment should be performed at baseline within 28 days before start of treatment and subsequently every 8 weeks of combination therapy (first restaging at the end of week 8), until progression of disease or end of treatment. All assessments should be performed within \pm 7 days of the scheduled day of assessment. The assessment at the end of treatment visit is only to be performed if the prior assessment occurred \geq 21 days before.⁹ Biopsies will be done at Screening, Cycle 1 Day 15, and within 14 days of any radiographic examination documenting disease progression by RECIST from all patients with visible or palpable disease unless the PI determines that a biopsy would pose an unacceptable risk to the patient.¹⁰ Echo/MUGA will be performed at baseline and every 4 cycles, or more often as clinically indicated.¹¹ ECG will be performed at baseline and (+/- 2 days) on cycle 1 day 15, on cycle 2, 3, and 4 day 1, and every 3 months thereafter in accordance with the manufacturer's standard-of-care recommendations for vemurafenib¹² Laboratory assessments including hematology, blood chemistries, and fasting blood glucose do not need to be repeated prior to the first dose of BKM120 if screening laboratories were performed within 72 hours of C1D1.¹³ If toxicity is present at C1D15, C1D22 visit may be done at the discretion of the physician.

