3.4.2 Efficacy assessments

Patients will undergo systemic imaging with a contrast-enhanced CT scan of the chest, abdomen, and pelvis (or a whole body PET/CT scan if this scan includes a CT resolution that is comparable to standard institutional protocols for CT alone) with 28 days prior to the initiation of therapy (baseline imaging) and on the last day of every even-numbered treatment cycle(+/- 3 days). Imaging assessments will be made by a radiologist, and final assessment using Response Evaluation Criteria in Solid Tumors (RECIST, version 1.1) will be made by the PI ^{37,38}. Any documentation of a PR or CR in a target or non-target lesion must be confirmed by a repeat scan at least 4 weeks after the initial scan indicating the PR or CR. The PI bears the final responsibility for determining tumor response and progression.

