5.2. Sample Size/Accrual Rate

This study will use the standard 3+3 dose escalation design to determine the RP2D of BKM120 in combination with vemurafenib (phase 1) followed by a single-stage binomial phase 2 design of 37 evaluable patients (any patient receiving at least 75% of prescribed cohort dose during the DLT period) to determine the PFS rate at 6 months.

For the Phase 1 portion

A Phase 1 dose escalation design using the standard 3+3 scheme will be followed and the sample size is not predetermined. We estimate the phase 1 portion of this trial will require a minimum of 2 patients from four predefined dose levels (see *Table 5*) to determine the phase 2 dose (MTD). The estimated maximum number of patients is 24. The final sample size of the study depends primarily on clinical considerations rather than on statistical considerations.

For the Phase 2 portion

The sample size for the phase 2 portion of this study is determined using single-stage binomial design for phase 2 studies. Preliminary data from trials of vemurafenibmonotherapy in advanced melanoma suggest a median PFS of approximately 6 months^{4,5,17}. The proposed design will be used to test the null hypothesis that the 6 month PFS rate of the study combination is 50% or less (which would not be clinically desirable) versus the alternative hypothesis that the true 6 month PFS rate is greater 70%, which would be considered clinically meaningful. The maximum total sample size will be 37 in Phase 2 including patients in the phase 1 portion of the study treated at the RP2D.

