5.3 Analysis Plan

All patients who received at least 75% of prescribed cohort dose during the DLT period will be considered evaluable. Patients not evaluable will be replaced.

Phase 1 portion of the study

Safety and tolerability will also be assessed by clinical review of all relevant parameters including adverse experiences (AEs), laboratory tests, and physical exam. Adverse experiences will be summarized as counts and frequencies for each dose level. Other safety endpoints will be summarized as appropriate. These data are descriptive in nature and statistical analysis tools will not be required. The recommended phase 2 dose will be determined using safety data including DLTs and post-DLT toxicity, the dose-response relationship, and PK data.

Pharmacokinetic data will be acquired as described in section 3.4.6 and average values and standard deviations at each time point will be reported.

Phase 2 portion of the study

The PFS duration is defined as the time from the date of start of protocol therapy to the date of the first documented progression or death due to any cause. A patient who has not progressed or died by the date of the analysis cut-off or when the patient received any further anticancer therapy would have the PFS censored at the time of the last adequate tumor assessment before the first of the cut-off date or of the anticancer therapy date. All patients will be followed for 6 months and proportion of patients that are progression free at 6 months will be calculated. We assume that combination treatment will have at least 70% PFS rate versus the undesirable PFS of <50% at 6 months. The phase 2portion is designed based single stage binomial design with the type I alpha of 5% and the power of 80%. If ≥ 23 patients ultimately achieve 6 months PFS, then further investigation of the drug is warranted.

As secondary efficacy endpoints, the median PFSand OS will be estimated using exact binomial distribution; time to progression will be estimated using Kaplan-Meier methods. The 6-month PFS and 95% confidence intervals will be reported. ORR will be reported as frequencies and proportions with exact 95% confidence intervals from the Binomial distribution. The frequencies of individual toxicities thought to be probably, possible, or definitely related to study drug will be reported as well as the incidence of any grade 3, 4, and 5 toxicities regardless of attribution.

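### Phase 2 promises 6-month status for every patient, but imaging stops when treatment stops, so patients who come off drug unprogressed lose the primary endpoint and cost power

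*Combined protocol and SAP*

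**What the plan says.** **Endpoint and decision.** Sections 5.1 and 5.3 carry the same sentence: "All patients will be followed for 6 months and proportion of patients that are progression free at 6 months will be calculated". Section 5.3 then sets the rule: "If ≥ 23 patients ultimately achieve 6 months PFS, then further investigation of the drug is warranted". Section 5.2 gives the denominator; the maximum total "will be 37 in Phase 2 including patients in the phase 1 portion of the study treated at the RP2D".

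**Who is counted.** Section 5.3: "All patients who received at least 75% of prescribed cohort dose during the DLT period will be considered evaluable". Only non-evaluable patients are replaced.

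**When scans happen.** Footnote 8 of Table 11c (phase 2), and the same footnote of Table 11a (phase 1 Part A), schedules imaging "subsequently every 8 weeks of combination therapy (first restaging at the end of week 8), until progression of disease or end of treatment". One further scan is possible: "The assessment at the end of treatment visit is only to be performed if the prior assessment occurred" at least 21 days before. Section 3.4.2 ties imaging to treatment cycles as well, "on the last day of every even-numbered treatment cycle(+/- 3 days"). Footnote 8 allows ±7 days.

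**After treatment.** Section 3.3.3 asks only for a 28-day visit from a patient stopped for a dose delay of more than 21 days. Section 3.3.4.2 gives 28 days of adverse-event follow-up, plus visits until an event that stopped treatment resolves or stabilizes. The text on monitoring BKM120 toxicities, within section 3.3.6.1.1, takes a patient needing more than two dose reductions off the study.

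**Censoring and medians.** Section 5.3 has, for patients without an event, "PFS censored at the time of the last adequate tumor assessment"; the sentence defines PFS duration. The same section estimates median PFS and OS from an exact binomial distribution, whereas section 5.1 names Kaplan-Meier.

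**The concern.** The follow-up promised in section 5 cannot be delivered by the schedule in section 3.4. RECIST progression needs imaging, and none is scheduled once treatment ends. The end-of-treatment scan settles status for someone who stops close to 6 months, but not for someone who stops in month 3.

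Patients who progress or die on study have a known outcome. The gap concerns the evaluable patient who stops all drug without progression, for example for toxicity after cycle 1. Evaluability depends on cycle 1 dosing alone, so this patient stays in the denominator.

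The primary analysis is a count against a fixed number, and a count has no censored category. Each such patient is a possible success that the trial gives up. The PTEN and phospho-S6 analyses in section 3.4.7 classify patients by the same 6-month status and inherit the gap.

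The estimation method for the medians is a separate, simpler defect: a binomial does not handle censored times.

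**Working it through.** **Inputs.** n = 37, null rate 0.50, alternative 0.70 (section 5.2); cut-off 23, alpha 5%, power 80% (section 5.3). The hypotheses are directional, so alpha is taken as one-sided. The number k of patients with unknown status is not in the documents; k = 1 and k = 2 are assumed.

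**Step 1: the plan's own figures.** With X ~ Bin(37, p):
- Cut-off 23: P(X ≥ 23 | 0.5) = 0.0939 and P(X ≥ 23 | 0.7) = 0.8870.
- Cut-off 24: P(X ≥ 24 | 0.5) = 0.0494 and P(X ≥ 24 | 0.7) = 0.8071.

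The sample size of 37 reproduces: it is the smallest exact design meeting 5% and 80%, with a cut-off of 24. The printed 23 does not give 5%. That is a separate issue, so both cut-offs are carried below.

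**Step 2: unknown status counted as not progression-free.** Only 37 − k patients can contribute successes. If patients with known status keep rate p, the chance of meeting cut-off c is P(Bin(37 − k, p) ≥ c).

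| Unknown k | Cut-off 23: alpha | Cut-off 23: power | Cut-off 24: alpha | Cut-off 24: power |
|---|---|---|---|---|
| 0 | 0.0939 | 0.887 | 0.0494 | 0.807 |
| 1 | 0.0662 | 0.837 | 0.0326 | 0.737 |
| 2 | 0.0448 | 0.773 | 0.0205 | 0.652 |

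**Step 3: unknown status excluded.** The cut-off is a number of patients, so exclusion leaves the numerator alone and gives the same decision as Step 2. With 21 known successes and 2 unknown, the count is 21 either way. Only the reported proportion moves: 21/37 = 56.8% against 21/35 = 60.0%.

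**Step 4: which scan is the 6-month scan.** Cycles are 28 days, so the end of cycle 6 is day 6 × 28 = 168, which is week 24. The next scan is at week 32, day 224. Six months is about day 183. The schedule therefore has no scan at 6 months exactly, and the plan does not say which one serves. The window around it is ±7 days in footnote 8 and ±3 days in section 3.4.2.

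**The case against.** The strongest reply is that the rule is already implied. A patient last scanned in month 3 has not been shown to reach 6 months without progression, so the wording in section 5.3 makes that patient a failure; exclusion would give the same decision. This stands. It removes most of the supposed ambiguity in the go/no-go decision, but it does not supply the missing scans or restore the power lost without them.

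A reader might infer more: that the silence could flip the verdict, since 21 known successes plus 2 unknown counted as progression-free makes 23, and alpha at that cut-off would rise to 0.155. The documents do not support this. No section suggests scoring an unassessed patient as progression-free, and the censoring sentence governs PFS duration, not the count.

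A reader might also take the number of such patients from section 1.4.2.2, where hyperbilirubinemia and hyperglycemia each led to discontinuation in 3.0% of the single-agent BKM120 study (2 of 66; 2/66 × 37 = 1.1). That does not carry over. Table 8 lets a patient who stops BKM120 for grade 4 hyperglycemia continue vemurafenib. The rates are single-agent, regardless of drug relationship, and give neither timing nor progression status.

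Finally, the 6-month sentence could be read as itself an instruction to keep assessing. Sites work from the visit schedule, however, and section 3.3.3 says that a 28-day visit is all some of these patients need.

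**Conclusion.** The contradiction is real and sits in the primary phase 2 endpoint: section 5 promises a status that the imaging schedule does not collect for evaluable patients who stop all drug unprogressed well before 6 months. The consequence is mainly avoidable loss of power, not an open door to a false positive; alpha falls along with power.

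The size depends on an assumed number of patients. One unknown costs about 5 percentage points of power at a cut-off of 23 (0.887 to 0.837) and 7 at 24 (0.807 to 0.737). Two cost about 11 (to 0.773) and 15 or 16 (to 0.652). At 24, a single unknown takes power below the planned 80%. These figures assume a true rate of 70% among patients with known status.

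The point is limited to patients who stop all study drug. The conflict over median PFS and OS is independent of it: section 5.3 names a method unsuited to censored times and contradicts section 5.1.

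**What to change.** **(a) Schedule.** In footnote 8 of Tables 11a and 11c and in section 3.4.2, state that patients who stop treatment without progression continue the existing 8-week imaging, counted from cycle 1 day 1, through the week-24 scan, or through the next scheduled scan if week 24 is missed, unless they progress or die first. Table 11a is included because Part A patients treated at the RP2D count toward the 37. Reconcile the ±7-day and ±3-day windows, and reconcile the follow-up wording in sections 3.3.3, 3.3.4.2 and 3.3.6.1.1 with the 6-month promise in section 5.

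**(b) Primary count.** In section 5.3:
- Name the week-24 scan, within the reconciled window, as the 6-month assessment.
- Count a patient as progression-free if that scan, or a later one if it was missed, shows no progression and there was no earlier progression or death.
- Count patients without such a scan, and patients who start new anticancer therapy before it, as not progression-free.
- Report Kaplan-Meier 6-month PFS under the existing censoring rule as a sensitivity analysis.

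**(c) Medians.** In section 5.3, estimate median PFS and OS by Kaplan-Meier with confidence intervals, as section 5.1 states. Keep the exact binomial for the 6-month proportion and ORR.

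**Cost.** (a) adds a few standard restaging scans in patients off drug. (b) and (c) are wording. Each patient whose status stays unknown still costs some power, and the scans in (a) keep that number small.

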3.4.2 Efficacy assessments

Patients will undergo systemic imaging with a contrast-enhanced CT scan of the chest, abdomen, and pelvis (or a whole body PET/CT scan if this scan includes a CT resolution that is comparable to standard institutional protocols for CT alone) with 28 days prior to the initiation of therapy (baseline imaging) and on the last day of every even-numbered treatment cycle(+/- 3 days). Imaging assessments will be made by a radiologist, and final assessment using Response Evaluation Criteria in Solid Tumors (RECIST, version 1.1) will be made by the PI ^{37,38}. Any documentation of a PR or CR in a target or non-target lesion must be confirmed by a repeat scan at least 4 weeks after the initial scan indicating the PR or CR. The PI bears the final responsibility for determining tumor response and progression.

3.4.3 Laboratory evaluations

Pregnancy Test

A serum pregnancy test (β -HCG) is required for all women of child-bearing potential at screening, within 72 hours prior to the first dose of BKM120. Note: Women are considered post-menopausal and not of child bearing potential if they have had 12 months of natural (spontaneous) amenorrhea with an appropriate clinical profile (e.g. age appropriate, history of vasomotor symptoms) or six months of spontaneous amenorrhea with serum FSH levels > 40 mIU/mL [**for US only**: and estradiol < 20 pg/mL] or have had surgical bilateral oophorectomy (with or without hysterectomy) at least six weeks ago. In the case of oophorectomy alone, only when the reproductive status of the woman has been confirmed by follow up hormone level assessment is she considered not of child bearing potential.

Hematology

Hematology includes the following parameters: complete blood count (CBC) consisting of red blood cell (RBCs), a total white blood cell count (WBC) with differential (total neutrophil count including bands, lymphocyte, monocyte, eosinophil, and basophil counts); hemoglobin (Hgb); and platelet count.

Coagulation Profile

The coagulation profile includes prothrombin time or INR, and activated partial thromboplastin time.

Blood chemistry

Biochemistry includes the following parameters: urea or blood urea nitrogen (BUN), creatinine, sodium, potassium, calcium, magnesium, phosphorus, glucose, albumin, total protein, total bilirubin (direct and indirect), amylase and lipase, GGT, alkaline phosphatase (fractionated if alkaline phosphatase is grade 2 or higher), bicarbonate, AST (SGOT), ALT (SGPT), and uric acid, lactic dehydrogenase (LDH), total cholesterol, high density lipoprotein (HDL), low density lipoprotein (LDL) and triglycerides are required at baseline and at end of treatment. Subsequent assessments always include K+, Na+, Ca++, ALT, AST, total bilirubin (direct and indirect), creatinine, alkaline phosphatase, bicarbonate, phosphorus, glucose, urea or BUN, albumin, and total protein BUT, lipase, total cholesterol, HDL, LDL, triglycerides should be obtained on the

first day of odd numbered cycles only. C1D-7assessments may be performed up to 72 hours prior to the scheduled visit. Cycle 1 draws may occur within 24 hours prior to the scheduled visit. All other draws should occur within 3 days of the intended visit. Because accurate serum glucose and lipid measurements are required; patients should be fasting at the time of the blood sampling.

Glucose monitoring (FPG, C-peptide, and HbA_{1C})

Fasting plasma glucose (FPG), C-peptide, and HbA_{1C} will be assessed. Patients must be fasting overnight for at least 8 hours prior to the blood draw. The study personnel will ask the patient whether he or she has been fasting, which will be captured in the eCRF as well.

HbA_{1c} and C-peptide will be measured at screening and on Day 1 of every third treatment cycle starting with Cycle 2 Day 1 and at EOT.

Urinalysis

Urinalysis includes macroscopic (protein, glucose, ketones, blood, and specific gravity) and will be performed at screening visit and EOT visit. A microscopic (WBC/HPF, RBC/HPF, and any additional findings) exam need only be performed if the urinalysis result is abnormal.

This must be supplemented with laboratory quantification of any potentially relevant abnormalities.

3.4.4 Clinical evaluations

3.4.4.1 Vital signs

Vital sign assessment consists of height (first visit), pulse, blood pressure, respiration rate, temperature and weight. Blood pressure, pulse and respiration rate should be measured on patients after at least 3 minutes in the sitting position

3.4.4.2 Physical examination

Physical examination will be performed which must comprise a total body examination (general appearance, skin, neck, including thyroid, eyes, ears, nose, throat, lungs, heart, abdomen, back, lymph nodes, extremities and basic nervous system).

Significant findings made after the start of study drug which meet the definition of an Adverse Event must be recorded.

3.4.4.3 Neuropsychiatric assessments

Patient self-rating mood questionnaires for anxiety and depression (PHQ-9, GAD-7) will be applied at:

- Screening
- Days 1 and 15 of Cycle 1
- Day 1 and 15 of Cycle 2
- Day 1 of Cycle 3 and subsequent cycles (only for patients who have not shown mood alterations during the first 2 cycles, patients who did should continue to fill out the questionnaire on a weekly base).

- End of Study treatment

Additional assessments may be done according to the clinical judgment of the Investigator. Symptomatic patients (\geq CTCAE grade 1) must continue with questionnaires on a weekly basis while active on the treatment portion of the study. Instructions on how to instruct the patient to complete the questionnaires as well as how to determine the scores will be provided together with each instrument.

3.4.4.4 Performance status

Performance status will be assessed at screening and per the visit schedule using the Eastern Cooperative Oncology Group (ECOG) performance scale.

3.4.5 Additional evaluations

3.4.5.1 ECG/ECHO

A standard 12 lead ECG is to be performed at screening and significant findings must be recorded. An echocardiogram (ECHO) or MUGA will be performed to assess eligibility. ECHO/MUGA will be repeated at Cycle 4 and then every 4th cycle thereafter.

3.4.5.2 Brain imaging

An MRI of the brain with gadolinium maybe performed during screening and patient with untreated or symptomatic brain metastases will be excluded from participation in this trial. Patients with asymptomatic, treated brain metastases with documented radiographic stability over at least 4 weeks may participate in this trial. For all patients enrolled on the trial, additional MRI imaging of the brain may be obtained as clinically indicated.

3.4.6 Drug levels and pharmacokinetic assessments

Data regarding the preclinical and clinical pharmacology of vemurafenib are presented in section 1.2.1.3 and 1.2.3 respectively. Data regarding the preclinical and clinical pharmacology of BKM120 are presented in section 1.4.1.3 and 1.4.2.1 respectively. All BKM120 pharmacokinetic analysis will be performed by Novartis (refer to Appendix 4 for details) and vemurafenib analysis will be performed at UCSF (refer to Appendix 5 for details).

Phase 1, Part A

Historical controls for PK of vemurafenib alone are well established and vemurafenib has minimal hepatic metabolism⁴. Pharmacokinetic measurements of serum levels of BKM120 after single dose will be made during a 7-day lead-in (day -7, $t = 0, 1, 2, 6$ hrs \pm 15 minutes; day -4 at 72 hrs post-dose \pm 1 hour). Serum levels of BKM120 and vemurafenib will be assessed on cycle 1 treatment day 1 ($t = 0, 1, 2, 6$ hrs \pm 15 minutes) and day 15 ($t = 0, \pm$ 1 hour) as well as trough levels ($t = 0 \pm$ 1 hour) on day 1 of cycles 2, 3, and 4. Vemurafenib is a weak CYP3A4 inducer and BKM120 is primarily metabolized by CYP3A4. Therefore, the effect of vemurafenib on BKM120 serum levels is of particular interest.

Phase 1, Part B

Serum levels of BKM120 and vemurafenib will be assessed on cycle 1 treatment days 1 ($t = 0, 1, 2, 6$ hrs \pm 15 minutes) and day 15 ($t = 0, \pm$ 1 hour) as well as trough levels ($t = 0 \pm$ 1 hour) on day 1 of cycles 2, 3, and 4.

Phase 1, Parts A & B

At each sample time point, two aliquots (2 mL each) of whole blood will be collected in EDTA blood collection tubes and the exact time of the dose and the blood draw will be noted. Detailed sample collection and shipping instructions are given in Appendices 4 and 5. Patients should take the daily doses of BKM120 and the first dose of vemurafenib in the morning. Patients must fast for at least 2 hours after a light breakfast (morning meal) before taking BKM120 and vemurafenib. Vemurafenib and BKM120 should be taken with a glass of water and consumed over as short a time as possible. Patients should swallow the capsules as a whole and not chew or crush them. Patients should continue to fast for 2 hours after the administration of the morning doses. PK measurements will be compared to historical controls for BKM120 and vemurafenib individually with the goal of comparing peak and trough exposure levels.

